2.4. Statistical Hypotheses / Statistical Analyses

The primary objectives of this study are to evaluate safety and tolerability of single and repeat doses of GSK3439171A and to characterize the PK of GSK3439171A. No formal statistical hypotheses will be tested. Descriptive statistics will be used to assess safety and tolerability objectives. Treatment comparisons with placebo will be based on review of descriptive statistics and individual participant data. An estimation approach will be used to address the PK objectives where point estimates and corresponding 90% confidence intervals (CIs) will be constructed as appropriate for the assessment of dose proportionality, steady-state, time invariance and food effect.

3. PLANNED ANALYSES

3.1. Interim Analyses

There will be no formal statistical interim analysis. However, preliminary safety, PK, and PD/biomarker data will be reviewed in-stream by the GSK study team members and investigational site (PAREXEL) team prior to each dose escalation. This data review is conducted in two steps: First GSK staff will review the unblinded data, as this is a sponsor unblinded trial and then the blinded data will be presented to investigational site team in another meeting. Data for these reviews will be cumulative and can include individual participant data, summaries by treatment group and graphical displays.

Preliminary results from available safety data may be reported prior to database freeze for the purposes of safety review by GSK, and where required by regulatory bodies. Other selected preliminary data may be unblinded and reported prior to database freeze for internal decision making. In each case described above, the study will not be officially unblinded and access to the randomization will be restricted.

After completing Part A and cohort 1&2 for Part B there was a safety review of the unblinded data to decide if higher dose can be administered for cohort 3 in Part B. Summaries and figures for Clinical chemistry, Hematology and Hormone level were created for the safety review (The displays that were created are indicated in list of data displays). Unblinded results were produced for an IB update, which was a subset of Study population, Safety and PK concentration displays, more details of the results submitted will be documented in IB update documentation.

Summaries and graphical displays for in-stream reviews will not be provided by Statistics and Programming and as such, no details on these summaries are provided in the RAP.

3.2. Final Analyses

Final analyses will be reported when all subjects in all cohorts have completed their final scheduled visits and the following sequential steps have occurred:

1. All participants have completed the study as defined in the protocol.
2. All required database cleaning activities have been completed and final database release (DBR) and database freeze (DBF) has been declared by Data Management.
3. All criteria for unblinding the randomization codes have been met.
4. Randomization codes have been distributed according to RandAll NG procedures.

4. ANALYSIS POPULATIONS

Population	Definition / Criteria	Analyses Evaluated
Screened	All participants who were screened for eligibility	Screen Failures
Randomized	All participants who were randomized	Study Population
Safety	All participants who take at least 1 dose of study intervention. Participants will be analyzed according to the intervention they actually received.	Study Population Safety
PK	Participants in the Safety population for whom a PK sample was taken and analyzed for GSK3439171A and result reported	PK
PD	Participants in the Safety population with at least one PD measure.	PD/Biomarker

Refer to [Appendix 12](#): List of Data Displays which details the population used for each display.
Metabolite ID work will be reported in a separate GSK report

4.1. Protocol Deviations

Important protocol deviations (including deviations related to study inclusion/exclusion criteria, conduct of the trial, patient management or patient assessment) will be summarised and listed.

Protocol deviations will be tracked by the study team throughout the conduct of the study in accordance with the Protocol Deviation Management Plan.

- Data will be reviewed prior to freezing the database to ensure all important deviations are captured and categorised on the protocol deviations dataset.
- This dataset will be the basis for the summaries and listings of protocol deviations.

A separate summary and listing of all inclusion/exclusion criteria deviations will also be provided. This summary will be based on data as recorded on the inclusion/exclusion page of the ClinBase.

5. CONSIDERATIONS FOR DATA ANALYSES AND DATA HANDLING CONVENTIONS

- There are no planned adjustments made for multiple centres in this study.
- There are no planned adjustments for multiple comparisons or multiplicity.

5.1. Study Treatment & Sub-group Display Descriptors

Treatment Group Descriptions			
RandAll NG		Data Displays for Reporting	
Code	Description	Description	Order in TLF
Part A			
D1	GSK3439171A Dose 1	5 mg	2
D2	GSK3439171A Dose 2	10 mg	3
D3	GSK3439171A Dose 3	30 mg	4
D4	GSK3439171A Dose 4	60 mg	5
D5	GSK3439171A Dose 5	120 mg	6
D6	GSK3439171A Dose 6	180 mg	7
PA	Placebo Part A	Placebo	1
Part B			
DD1	GSK3439171A R1 mg QD or BID	5 mg	10
DD2	GSK3439171A R2 mg QD or BID	11 mg	11
DD3	GSK3439171A R3 mg QD or BID	40 mg	12
PB	Placebo Part B	Placebo	8
PB3	Placebo Part B Cohort 3	Placebo Cohort 3	9

Treatment Group Descriptions			
RandAll NG		Data Displays for Reporting	
Code	Description	Description	Order in TLF
Part C			
C1	GSK3439171A fasted	60 mg Fasted	13
C2	GSK3439171A fed	60 mg Fed	14

Note: If additional dose levels are explored in either Part A or B, then they will follow in a sequential order in the table

Treatment comparisons will be displayed as follows using the descriptors as specified:

1. Day 17 vs Day 1 (e.g.; Ro, RCmax and Rss)
2. Dose X.X mg vs Placebo
3. Repeat Dose X.X mg vs Placebo
4. Fasted vs Fed

5.2. Baseline Definitions

For all endpoints (except as noted in baseline definitions) the baseline value will be the latest pre-dose assessment with a non-missing value, including those from unscheduled visits. For the parameters having multiple assessments, mean value of the assessments will be considered as baseline value.

Baseline Definitions – Part A

Parameter	Study Assessments Considered as Baseline				Baseline Used in Data Display
	Screening	Day -2	Day -1	Day 1 (Pre-Dose)	
Safety Assessments					
Lab results, 12-lead Electrocardiogram (ECG) & Vital Signs	X	X		X	Day 1
Routine Urinalysis	X			X	Day 1
Telemetry				X	Day 1 30 min (\pm 10 min)
Pharmacodynamics parameters			X	X	Day -1 #

Postdose value will be collected on intervals 0-2, 2-4, 4-6, 6-8, 8-12 and 12-24 hr. Time matched predose value for each of these intervals (24-22, 22-20, 20-18, 18-16, 16-12 and 12-0 respectively), predose aggregate value of 24-12hr (for post dose aggregate of 0-12 hrs) and predose aggregate value of 12-0 hr (for post dose aggregate of 12-24 hrs) will be considered as baseline for different pharmacodynamic parameters

Baseline Definitions – Part B

Parameter	Study Assessments Considered as Baseline				Baseline Used in Data Display
	Screening	Day -2	Day -1	Day 1 (Pre-Dose)	
Safety Assessments					
Lab results	X	X	X	X	Day 1
Hormone monitoring			X		Day -1 [†]
Routine Urinalysis, 12-lead Electrocardiogram (ECG) & Vital Signs	X	X		X	Day 1
Telemetry				X	Day 1 30 min (\pm 10 min)
Pharmacodynamics parameters			X	X	Day -1 #
Blood sampling for metabolite profiling				X	Day 1 (pre-dose)
Muscle Biopsy			X		Day -1

[†] There will be 2 individual baseline values (samples from midnight and 9am) for ACTH and Cortisol hormones. Both values may be used to calculate change from baseline for post dose measurements.

Postdose value will be collected on intervals 0-2, 2-4, 4-6, 6-8, 8-12 and 12-24hr. Time matched predose value for each of these intervals (24-22, 22-20, 20-18, 18-16, 16-12 and 12-0 respectively), predose aggregate value of 24-12hr (for post dose aggregate of 0-12 hrs) and predose aggregate value of 12-0 hr (for post dose aggregate of 12-24 hrs) will be considered as baseline for different pharmacodynamic parameters

Baseline Definitions – Part C

Parameter	Study Assessments Considered as Baseline			Baseline Used in Data Display
	Screening	Day -1	Day 1 (Pre-Dose)	
Safety Assessments				
Lab results, 12-lead Electrocardiogram (ECG) & Vital Signs	X		X	Day 1
Routine Urinalysis	X		X	Day 1
Telemetry			X	Day 1 30 min (\pm 10 min)

Unless otherwise stated, if baseline data is missing no derivation will be performed and baseline will be set to missing.

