Safety Laboratory assessments (include liver chemistries)	X	X			X			X ¹		X ¹						X ¹			X		(X)	X ¹	Pre-randomization assessments for eligibility must be performed PRIOR to predose muscle biopsy Predose, 24 hr, and 48, and 72 hr post-Day 1 dose; additional timepoints may be added based on findings in Part A ¹ Days 7, 11, 17, 20, and follow-up
Routine urinalysis	X	X			X			X ²		X ²						X ²			X ²		(X)	X ²	Predose, 24 hr, 48 hr, and 72 hr post-Day 1 dose; additional timepoints may be added based on findings in Part A ² Days 7, 11,17, 20, and follow-up

Part B – Repeat Dose																						
Procedure	Screening (up to 30 days before Day 1)	Intervention Period [Days] (for each dosing cohort)																		E.D	Follow-up (~14± 1 days post last dose)	Notes E.D = early discontinuation/withdrawal
		-2	-1	1	2	3	4	5-7	8	9-11	12	13-14	15	16	17	18	19	20				
12-lead ECG	X	X																		(X)	X	
ECGs assessed at screening (triplicate measure) and admission (single measure). During treatment period ECGs assessed predose (triplicate measure at at least 5 min intervals) and post-dose (single measure) every 30 min for 1 hr, hourly up to 6 hr, at 12 hr post-dose then at 24 hr, 36 hr, 48 hr, and 72 hr post-dose
 
⁵ Days 7, 11, 15, and 17, and 20 Post-dose at Cmax based on observed Cmax in Part A (currently estimated to occur at ~2 hr post dose), except for Day 20. Day 20 ECG to occur any time before Discharge

Part B – Repeat Dose																						
Procedure	Screening (up to 30 days before Day 1)	Intervention Period [Days] (for each dosing cohort)																	E.D	Follow-up (~14± 1 days post last dose)	Notes E.D = early discontinuation/withdrawal	
		-2	-1	1	2	3	4	5-7	8	9-11	12	13-14	15	16	17	18	19	20				
Vital signs (pulse rate, bp, respiratory rate, and oral temperature)	X	X																		(X)	X	
⁶Vitals assessed at screening (triplicate measurements for pulse and bp) and admission (single measurements). During treatment period vitals assessed predose (triplicate measurements for pulse and bp) and postdose (single measurements) every 15 min for 1 hr, hourly up to 6 hr, and at 12 hr, 24 hr, 36 hr, 48 hr, and 72 hr post-dose
 
⁷Vitals assessed once every 24 hr
 
See Section 8.2.2 for further information

Randomization				X																		

Part B – Repeat Dose																													

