Procedure	Screening (up to 30 days before Day 1)	Intervention Period [Days] (for each dosing cohort)															E.D	Follow-up (~14±1 days post last dose)	Notes E.D = early discontinuation/withdrawal
		-2	-1	1	2	3	4	5	6	7	8	9	10	11	12	13			
Muscle Biopsy			X ¹⁴													X ¹⁵		(X)	Muscle biopsies must be performed AFTER clinical safety assessments on the corresponding days ¹⁴ Day -1 muscle biopsy to occur 1-6 hr after estimated timing of initial dose on Day 1. Time of sample collection to be recorded ¹⁵ Day 10 muscle biopsy to occur within 1-6 hr after last dose administered Time of sample collection to be recorded. Muscle biopsy can be performed at any time during pre-dose period.
Discharge from Clinical Unit																	X	(X)	

- The time to start the second dose in Part B can be modified based on the estimates of half-life from Part A.
- Duration of dosing in Part B can be modified based on the estimates of half-life from Part A.
- The timing and number of planned study assessments, including safety, PK, PD/biomarker or other assessments may be altered during the course of the study based on newly available data (e.g., to obtain data closer to the time of peak plasma concentrations) to ensure appropriate monitoring.
- Any changes in the timing or addition of time points for any planned study assessments as the result of emerging pharmacokinetic/pharmacodynamic data from this study must be documented and approved by the relevant study team member and then archived in the sponsor and site study files, but will not constitute a protocol amendment. The CA and EC will be informed of any safety issues that constitute a substantial amendment and require alteration of the safety monitoring scheme or amendment of the ICF. The changes will be approved by the CA and the EC before implementation.

Part C- Food Effect									
	Screening (up to 30 days before Day 1)	Treatment Period [Days] (with or without food)					E.D.	Follow- up (~14±1 days post last dose)	Notes E.D = early discontinuation/withdrawal
		-1	1	2	3	4			
Informed consent	X								
Inclusion and exclusion criteria (including drug screens)	X		X						Recheck clinical status before randomization and/or 1st dose of study medication.
Demography	X								
Physical examination including height and weight	F	B				B	(B)	F	F: Full exam; B: Brief Exam; height is only taken once at screening

Part C- Food Effect									

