Participants will report to the Clinical Research Unit on Day -2 and will remain in the unit for the duration of Part B. Participants will randomly be assigned to receive a single dose (or a BID dose depending on data obtained in Part A) of GSK3439171A or placebo (approximately 9 study intervention: 3 placebo). Plasma and urine PK, PD, and biomarker samples (including a pre-dose muscle biopsy) will be collected for up to 72 hr after initial dosing. After completion of assessments at 72 hr (Day 4), participants will begin a repeat dosing regimen consisting of one dose (or a BID dose depending on data obtained in Part A) per day for up to 14 days. This time period is based on a predicted half-life of GSK3439171A of 6.1 hours (with a range of 4-22 hours) calculated from preclinical data and is designed to allow GSK3439171A to reach steady state during the dosing period. The actual repeat dose duration can be altered based on PK data in Part A of the study. For example, if the predicted half-life is confirmed from Part A of the study then the duration of dosing in Part B will be much shorter to achieve steady-state than planned currently. Dosing duration in Part B and follow-up will be shortened appropriately based on emerging PK data from Part A. Participants will be discharged on the morning of Day 13 (3 days post last dose during the 7 day repeat dose period) or Day 20 (3 days post-last dose during the 14 day repeat dose period) following completion of study assessments, including a post-dose muscle biopsy. Safety, tolerability and PK data review for a minimum of 6 participants receiving active treatment will be carried out upon completion of assessments on Day 13 or 20 (72 hours post-last dose) before initiation of dosing in the next cohort. The dose of GSK3439171A may be adjusted (lower or higher) based on data from Part A and for cohorts going forward based upon the safety, tolerability, PK, and preliminary PD data from the previous cohort.

All participants will return to the clinical unit for a follow-up visit approximately 14 days following the administration of the last dose of study medication.

Part C: Food Effect

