Any changes in the timing or addition of time points for any planned study assessments as the result of emerging pharmacokinetic/pharmacodynamic data from this study must be documented and approved by the relevant study team member and then archived in the sponsor and site study files, but will not constitute a protocol amendment. The CA and EC will be informed of any safety issues that constitute a substantial amendment and require alteration of the safety monitoring scheme or amendment of the ICF. The changes will be approved by the CA and the EC before implementation.

Part B .2- 7 Day Repeat Dose																					
Procedure	Screening (up to 30 days before Day 1)	Intervention Period [Days] (for each dosing cohort)															E.D	Follow-up (~14±1 days post last dose)	Notes E.D = early discontinuation/withdrawal		
		-2	-1	1	2	3	4	5	6	7	8	9	10	11	12	13					
Informed consent	X																				
Inclusion and exclusion criteria (including drug screens)	X	X																		Recheck clinical status before randomization and prior to muscle biopsy/or 1st dose of study medication.	
Demography	X																				
Full physical examination including height and weight	F	B																B	(B)	F	F: Full exam; B: Brief exam; height is only taken once at screening
Medical history (includes substance usage and family history of premature CV disease and any changes in health status occurring between screening and admission to the unit)	X	X																			Substances: Drugs, Alcohol, tobacco, and caffeine

Part B .2- 7 Day Repeat Dose																					
Procedure	Screening (up to 30 days before Day 1)			Intervention Period [Days] (for each dosing cohort)													E.D	Follow-up (~14±1 days post last dose)	Notes E.D = early discontinuation/withdrawal		
				-2	-1	1	2	3	4	5	6	7	8	9	10	11				12	13
Past and current medical conditions	X	X																			
HIV, Hepatitis B and C screening	X																		If test otherwise performed within 3 months prior to first dose of study intervention, testing at screening is not required		
Admission to Clinical Unit		X																			
Safety Laboratory assessments (include liver chemistries)	X	X			X							X ¹						X ¹	(X)	X ¹	Pre-randomization assessments for eligibility must be performed PRIOR to predose muscle biopsy Predose, 24 hr, and 48, and 72 hr post-Day 1 dose; additional timepoints may be added based on findings in Part A ¹ Days 7, 10, 13, and follow-up

Part B .2- 7 Day Repeat Dose																				

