3.20.	Safety	LB1	Summary of Chemistry Changes from Baseline - Part A	By dose and 'All Treatment' for all parameters mentioned in the protocol Includes Baseline values. Includes pre-specified parameters repeated in conventional units.	SR, SAC

Safety: Tables					
No.	Population	IDSL / Example Shell	Title	Programming Notes	Deliverable [Priority]
3.21.	Safety	LB1	Summary of Chemistry Changes from Baseline - Part B	By dose for all parameters mentioned in the protocol Includes Baseline values. Includes pre-specified parameters repeated in conventional units.	SR, SAC
3.22.	Safety	LB1	Summary of Chemistry Changes from Baseline - Part C	By treatment group (fed/fasted) and 'Total' for all parameters mentioned in the protocol Includes Baseline values. Includes pre-specified parameters repeated in conventional units.	SAC
3.23.	Safety	LB1	Summary of Chemistry Percent Changes from Baseline - Part A	By dose and 'All Treatment' for all parameters mentioned in the protocol Includes Baseline values. Baseline values are required Includes pre-specified parameters repeated in conventional units.	SAC
3.24.	Safety	LB1	Summary of Chemistry Percent Changes from Baseline - Part B	By dose for all parameters mentioned in the protocol Includes Baseline values. Baseline values are required Includes pre-specified parameters repeated in conventional units.	SAC

Safety: Tables					
No.	Population	IDSL / Example Shell	Title	Programming Notes	Deliverable [Priority]
3.25.	Safety	LB1	Summary of Chemistry Percent Changes from Baseline - Part C	By treatment group (fed/fasted) and 'Total' for all parameters mentioned in the protocol Includes Baseline values. Baseline values are required Includes pre-specified parameters repeated in conventional units.	SAC
Laboratory: Haematology					
3.26.	Safety	LB1	Summary of Haematology Values – Part A	By dose for all parameters mentioned in the protocol	SR, SAC
3.27.	Safety	LB1	Summary of Haematology Values – Part B	By dose for all parameters mentioned in the protocol	SR, SAC
3.28.	Safety	LB1	Summary of Haematology Values – Part C	By treatment group (fed/fasted) and 'Total' for all parameters mentioned in the protocol	SAC
3.29.	Safety	LB1	Summary of Haematology Changes from Baseline - Part A	By dose and 'All Treatment' (treatment vs placebo) for all parameters mentioned in the protocol	SR, SAC
3.30.	Safety	LB1	Summary of Haematology Changes from Baseline - Part B	By dose for all parameters mentioned in the protocol	SR, SAC

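### In Part B, change from baseline in creatine kinase starts from a Day 1 value drawn after the Day -1 muscle biopsy, which can lower the within-arm change and shrink the percent contrast with placebo

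*SAP*

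**What the plan says.** **Baseline.** The general rule in SAP 5.2 is "the baseline value will be the latest pre-dose assessment with a non-missing value, including those from unscheduled visits". The Part B row reads "Lab results X X X X Day 1": Screening, Day -2, Day -1 and Day 1 pre-dose are all eligible, and the displays use Day 1. The same table has "Muscle Biopsy X Day -1". Hormones and pharmacodynamic parameters are given a Day -1 baseline. CK has no entry of its own.

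**Biopsy.** Protocol 4.1 describes Part B in general, active and placebo alike: "biomarker samples (including a pre-dose muscle biopsy) will be collected". The 7-day schedule (Protocol 1.3) has "Day -1 muscle biopsy to occur 1-6 hr after estimated timing of initial dose on Day 1", and its note then permits the biopsy at any pre-dose time.

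**Laboratory draws.** Safety laboratory samples are scheduled at admission on Day -2, and then "Predose, 24 hr, and 48, and 72 hr post-Day 1 dose". There are two ordering rules. One is "Pre-randomization assessments for eligibility must be performed PRIOR to predose muscle biopsy". The other places a biopsy after the safety assessments of the same day.

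**Displays.** Total creatine phosphokinase is in the chemistry panel (Protocol Appendix 2, Table 3). It therefore enters SAP Table 3.21, "Summary of Chemistry Changes from Baseline - Part B", its percent counterpart Table 3.24, and the mean change plots in Figures 3.7 and 3.10. Table 3.21 is also marked for the safety review that SAP 3.1 describes, which considered whether cohort 3 could receive a higher dose.

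**The concern.** Neither ordering rule covers the Day 1 pre-dose draw. One protects the eligibility samples, the other protects samples taken on the day of the biopsy. The baseline rule then selects the value drawn after a sample of thigh muscle has been removed, although a value from before the biopsy is already collected on Day -2.

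CK is the chemistry analyte for which this order matters most, because it is a muscle enzyme. If the biopsy raises it, every arm starts high and drifts down as the effect fades, and a rise on drug can then read as little or no change. Laboratory values are a primary safety endpoint, and Protocol 2.2.1 presents the drug as acting on muscle repair, so the CK rows will be read with interest.

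**Working it through.** The plan gives no CK mean, SD or biopsy effect, so there is no figure of its own to reproduce. The check has three parts.

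**1. Order of events.** In the 7-day schedule the biopsy falls 1 to 6 h after the dosing clock time, one day early. The interval to the first dose is 24 - 6 = 18 h to 24 - 1 = 23 h. The any-time clause means it may vary between participants. For the 14-day cohorts, the order (Day -1 biopsy, Day 1 baseline) rests on Protocol 4.1 and the SAP 5.2 table, because the biopsy row of that schedule is not visible in the available text.

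**2. Effect on the displays.** Let C be resting CK, f the proportional rise from the biopsy at the Day 1 draw, and g the true on-treatment multiple. Suppose the biopsy effect has gone by the on-treatment visit.
- Baseline: B = C(1+f)
- Active change: C(g-1-f), or (g-1-f)/(1+f) as a proportion
- Placebo change: -Cf, or -f/(1+f) as a proportion
- Active minus placebo: C(g-1) on the absolute scale, (g-1)/(1+f) on the percent scale

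Assumptions, none of them from the documents: C = 150 U/L, g = 2, and f over a range.

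| f | Baseline (U/L) | Active change | Placebo change | Absolute contrast (U/L) | Percent contrast (points) |
|---|---|---|---|---|---|
| 0 | 150 | +150 (+100%) | 0 (0%) | 150 | 100 |
| 0.1 | 165 | +135 (+82%) | -15 (-9%) | 150 | 91 |
| 0.25 | 187.5 | +112.5 (+60%) | -37.5 (-20%) | 150 | 80 |
| 0.5 | 225 | +75 (+33%) | -75 (-33%) | 150 | 67 |
| 1 | 300 | 0 (0%) | -150 (-50%) | 150 | 50 |
| 2 | 450 | -150 (-33%) | -300 (-67%) | 150 | 33 |

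The within-arm change is zero when f = g - 1 and negative when f is larger. The absolute contrast is the same in every row. The percent contrast is multiplied by 1/(1+f).

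**3. Precision of the placebo comparison.** With about 9 active and 3 placebo participants in a cohort, the standard error of a difference in means is sqrt(1/9 + 1/3) = 0.67 SD. SAP 5.1 has one Part B placebo group plus a separate cohort 3 placebo group. For the first two dose levels the comparator is therefore about 6, and the standard error is sqrt(1/9 + 1/6) = 0.53 SD.

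**The case against.** The case on the other side is substantial, and most of it stands.

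- **The premise is assumed.** No section says that the biopsy raises CK, by how much or for how long. The procedure risks in Protocol 2.3.1 are pain, bleeding, infection and nerve damage. At f = 0.1 a doubling still reads +82%.
- **Much of the plan does not use this baseline.** Under SAP 13.6.1 the Part B absolute-value displays include Screening and Day -2. Table 3.18 shows those values by dose and was also part of the safety review. Figure 3.2 plots individual values. Listings 72 and 75 use the absolute flag above 500 U/L.
- **Placebo participants have the same biopsy**, and randomization follows it on Day 1. The absolute-change contrast is unbiased, only imprecise.
- **The stakes are limited.** Protocol 2.3.1 lists liver, adrenal and female reproductive risks, not muscle, and no stopping rule uses CK change.
- **A Day -2 baseline moves the bias.** If a proportional rise r remains on Days 2 to 4, a participant with no drug effect reads -C(f-r) from Day 1 but +Cr from Day -2.

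Two things remain. Comparison with placebo does not restore the percent contrast. And the flag, though unbiased, may not react: with C = 150, a tripling gives 450 U/L, which is below 500.

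**Conclusion.** The point holds in a limited form. A stated rule starts CK change in Part B from a post-biopsy value. If the biopsy raises CK, the within-arm change in Tables 3.21 and 3.24 and Figures 3.7 and 3.10 is biased downward, and the percent contrast with placebo shrinks by 1/(1+f). Both the existence and the size of f are assumptions; over f = 0.1 to 2 the result runs from trivial to a reversed sign.

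Three stronger readings are tempting, and the documents do not support them.
- A reader might infer that a CK signal would be missed. It would be obscured in the change displays, but absolute values including Day -2 are shown.
- A reader might infer that the placebo comparison as a whole is biased. On the absolute scale it is not.
- A reader might infer that individual review works from each participant's own change. SAP 7 speaks only of individual data, and the planned individual chemistry figure and listings show values.

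Nor can 18 to 23 h be taken as the interval for all of Part B. The safety review that used Table 3.21 covered cohorts 1 and 2, whose biopsy clock time could not be read. SAP 3.1 reports that review as already held, so the correction serves the final reporting.

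**What to change.** In the Part B table of SAP 5.2, give CK its own row, with baseline defined as the last non-missing value before the Day -1 biopsy, normally the Day -2 admission sample. Tying it to the biopsy rather than to a fixed day also covers the any-time clause. Keep the Day 1 pre-dose baseline as a sensitivity display. In Tables 3.21 and 3.24 and Figures 3.7 and 3.10, footnote every CK value that may carry a biopsy effect: Day 1 pre-dose, Days 2 to 4, and values drawn after the end-of-dosing biopsy, such as Day 13 in the 7-day cohort.

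The cost is one row, a set of footnotes and one extra display; no new sample is needed. There are two downsides. CK will have a different baseline day from the rest of the panel. And any biopsy rise still present on Days 2 to 4 will appear as an increase in every arm, so those days must be read against placebo.
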